8.3.2.2 FVIII inhibitors

...

If the Investigator decides to send a sample for inhibitor testing to a local laboratory, the Investigator must also send a duplicate sample for inhibitor testing to the Central Laboratory. The data from the Central Laboratory will then be used in the official analysis. *Any single A-positive inhibitor test must be reported as a MESI (please refer to section 12.1.2).*

...

A patient having an initial positive inhibitor ~~positive~~ test and a second negative inhibitor test, *will be regarded as inhibitor negative and can ~~will be reported as a MESI and~~ continue in the trial.*

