18.5 Interim Analysis

...

All data from the Main Phase of the trial will be analysed and reported when all patients have reached *at least 50 EDs* (except for patients having had surgery as part of pathfinder™ 3), *and all patients have had their first visit after 50 EDs where all planned assessments including inhibitors have been performed. The analysis of the main phase of the trial will be based on all data up to the patient's last visit at this point.* All main conclusions from the trial will be based on this reporting. Furthermore, an interim analysis will be performed when the patients enrolled in the randomised part of the Extension have completed part 1.

Protocol Amendment
No 15
to Protocol, final version 8.0
dated 12 July 2013

pathfinder™ 2

Trial ID: NN7088-3859

**A Multi-national Trial Evaluating Safety and Efficacy,
including Pharmacokinetics, of NNC 0129-0000-1003 when
Administered for Treatment and Prophylaxis of Bleeding in
Patients with Haemophilia A**

Trial phase: 3

Applicable to all countries

Amendment originator:

This ~~confidential~~ document is the property of Novo Nordisk. ~~No unpublished information contained herein may be disclosed without prior written approval from Novo Nordisk. Access to this document must be restricted to relevant parties.~~

Table of contents "Double click to update Table of Content"

	Page
1 Introduction including rationale for the protocol amendment	3
2 Changes	4

1 Introduction including rationale for the protocol amendment

The VHP requested that patients in the every 7 days treatment arm (Q7D) receive the same visit schedule as patients in the every 4 days treatment arm (Q4D) of the Main Study Phase i.e. monthly visits at the start of treatment, followed by visits every second month.

In addition, it was agreed with the VHP to also implement this visit schedule for patients randomised to Q4D in the extension phase part 1. This is to avoid any bias in the randomised arms. Part 1 of the extension is 6 months in duration, therefore monthly visits for the first 4 months have been introduced, followed by a visit 2 months later.

The VHP stipulated that this visit schedule should apply for every switch to Q7D independent of the part of the extension phase. Therefore, this requirement has also been implemented for Q7D patients in Part 2 of the extension. In Part 2, those switching to Q7D, will have visits every month for the first 4 months and subsequently every two months while on Q7D.

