5.3.1 Prophylaxis

...

[figure not shown]
Extension Phase part 2: During this period it is possible to change the prophylaxis treatment of patients to every 4 day or 7 day treatment. For deciding to change a regimen the Investigator must monitor the patient on an on going basis and follow the below rules:

- 0-2 bleeding episodes within last 6 months on same regimen allow a less frequent dosing interval of every 7 day. Change to a less frequent treatment regimen should be done while the patient is at a site visit. *After switching, the patient must attend the next sequential a-visit in line. The a-visits are applicable to attend 2 times following a switch to every 7 day treatment regimen to allow for monthly visits the first 4 months and thereafter visits every second month while on every 7 day treatment regimen, see Table 2-3 and Figure 8-2*
- If a patient on every 7 day treatment regimen over a 8 week period experiences two or more spontaneous bleeding episodes or one severe bleeding episode requiring hospitalisation, then the patient must be switched back to every 4 day treatment regimen. *The patient must attend the next sequential visit in line and attend visits every third month while on every 4 day treatment regimen, see Table 2-3 and Figure 8-2.*

[figure not shown]
8 Methods and Assessments

...

Old figure 8-2:

New figure 8-2

OD = on-demand, PPX = prophylaxis, BE = bleeding episodes, ® = randomisation, Q4D = prophylaxis every 4 day, Q7D = prophylaxis every 7 day, w = weeks, ○ 2 consecutive a-visits are mandatory to attend upon switching to Q7D in order to achieve visits every 4 weeks (± 1 week) during the first 4 months

...

The Extension Phase part 1 will include the following visits:

- *Non-randomised prophylaxis and on-Demand patients*
Visit 14 (same date as Visit 13 (EOM)): patients are enrolled in Extension Phase
Visit 15+16: Visits at the site
 - ~~Patients in the randomised treatment arms~~ will be dosed during the visits
 - Patients on prophylaxis NOT in the randomised treatment arm will be dosed during the visits
 - Patients on the on-demand treatment arm will not be dosed during the visits
- *Randomised PPX patients*
Visit 14 (same date as Visit 13 (EOM)): patients are enrolled in Extension Phase
Visit 14a, 15, 15a +16: Visits at the site
 - Patients in the randomised treatment arms will be dosed during the visits

The Extension Phase part 2 will include the following visits:

- Visit 17-n** : Visit at site

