Visit 17a-visits-n: 2 consecutive a-visits are mandatory to attend upon switching to every 7 day treatment regimen in order to achieve visits every 4 weeks (± 1 week) during the first 4 months
- Dosing regimen will be considered
 - Patients on prophylaxis regimen will be dosed at visits
- Patients on the on-demand arm will not be dosed during the visits

...

8.1.4 Visit 14-n and EOT Visit- visit in the Extension Phase of the trial

...

The numbers of bleeding episodes should be counted before all visits from visit 13 in preparation for a potential change in dosing regimen, *see section 5.3.1.*

The home treatment period for patients on *non-randomised every 4 day* prophylaxis and on-demand is approximately 8 weeks (± 2 week) between visits during the first 4 visits in the Extension phase part 1 (Visit 14-17). *The home treatment period for patients randomised to every 4 or 7 day prophylaxis in Extension phase part 1 is 4 weeks (± 1 week) for the first 4 months and thereafter 8 weeks (± 1 week) (Visit 14-17), see Table 2-3.*

The home treatment period for patients on every 4 day and twice weekly prophylaxis, and on-demand is ~~and~~ 12 weeks (± 2 weeks) ~~apart~~ in the Extension phase part 2 (from the Visit 17). Patients continuing on every 7 day prophylaxis from Extension phase part 1 into Extension phase part 2, will continue a home treatment period of 8 weeks (± 1 weeks). Whenever a patient in Extension phase part 2 switches to every 7 day prophylaxis, the home treatment period will be 4 weeks (± 1 weeks) for the first 4 months and thereafter 8 weeks (± 1 week) for the remaining of the period on every 7 day prophylaxis, see Table 2-3.

...

The following will be performed and/or recorded in the eCRF at all visits during the Extension Phase:

...

~~Telephone Contact:~~

~~It is recommended that a phone call is made to patients at the 4 or 6-week interval between the site visits.~~

Protocol Amendment
Trial ID: NN7088-3859
UTN: U1111-1119-7416
EudraCT No.: 2011-001142-15

~~CONFIDENTIAL~~

Date:
Version:
Status:
Page:

27 September 2013
1.0
Final
1 of 6

Novo Nordisk

Protocol Amendment
No 16
to Protocol, final version 9.0
dated 28 August 2013

NN7088-3859

**A Multi-national Trial Evaluating Safety and Efficacy, including Pharmacokinetics, of NNC
0129-0000-1003 when Administered for Treatment and Prophylaxis of Bleeding in Patients
with Haemophilia A**

Trial phase: 3

Applicable to US site 924

Amendment originator:

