Only treatment requiring bleeding episodes will be considered in the above evaluations of ABR. Incidence rate of FVIII-inhibitor and haemostatic effect of N8-GP when used for treatment of bleeding episodes will be evaluated based on accumulated data (Main Phase + Extension Phase part 1).

Adverse events, consumption of N8-GP, recovery and pre-dose levels will be summarised based on accumulated data (Main + Extension Phase part 1) by treatment regimen combining the every 4 day dosing regimens. In addition, separate summaries including data from part 1 only will be presented by treatment regimen for the randomised subset of patients to support the main objective of part 1 of the Extension Phase.

Other safety endpoints will be summarised based on accumulated data (Main Phase + Extension Phase part 1). Binding non-inhibitory antibodies will be listed.

PRO endpoints at end the Extension Phase part 1 will be evaluated and presented as described in section 18.9.

Data from part 2 of the Extension Phase

The main objective of extension phase part 2 is to collect long term safety and efficacy data.

ABR will be calculated as for the co-primary endpoint in the main phase, but based on the accumulated data, i.e. combined data from main phase, extension phase part 1 and extension phase part 2. Furthermore, sensitivity analyses are performed based on actual bleeding episodes and exposure times (i.e. without imputation for withdrawn patients).

Incidence rate of FVIII-inhibitor and haemostatic effect of N8-GP when used for treatment of bleeding episodes will be evaluated based on accumulated data.

Adverse events and consumption of N8-GP will be summarised based on accumulated data by treatment regimen.

Incremental recovery will be summarised by visit for extension phase part 2 and furthermore be presented graphically in the following ways:

- By N8-GP production process (extension phase part 2 data)
- According to Anti-PEG-antibody status (accumulated data)

For Anti-CHO HCP-antibodies, the number of negative/positive samples will be summarised by visit.

Other safety endpoints will be listed and/or plotted based on accumulated data.

-

PRO endpoints for extension phase part 2 will be summarised by time since first dose (since timing of visits depend on treatment regimen). Time grouping will span a year, i.e. grouping being “1 - <2 years”, “2 - <3 years”,.... The two prophylaxis regimens will be considered as a combined prophylaxis treatment regimen.

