Calculation of ABR by month for a given treatment regimen has been defined to be based on the first consecutive period on the treatment regimen to ensure that a effect over time is not influenced by time on other treatment regimens.

Calculation of ABR by calendar month has been defined to be done by shifting calendar month half a year for countries in the southern hemisphere (i.e. Brazil and Australia). This is done to take the difference in seasons between the southern and northern hemisphere into account.

The ABRs defined to be calculated based on a sub-selection consisting of data from extension phase part 2, will not be done, since patients have differing trial durations when entering extension phase part 2 and therefore ABRs for such a sub-selection is of limited value.

PK data:

Since patients are allowed to change treatment regimen at any time during the extension phase part 2 and since the visits intervals are different for the prophylaxis treatment regimens, FVIII activity data will be summarised by visit only for incremental recovery. Since incremental recovery is dose-normalised activity increase this will not be affected by a possible regimen and dose change.

Plots of pre-dose activity measurements will not be created since the plots have been evaluated to contribute with no relevant information.

PRO data:

PRO endpoints for extension phase part 2 will be summarised by grouping of time since first dose, since timing of visits depend on treatment regimen and since patients are moving between treatment regimens.

Safety data:

Adverse Events and Serious Adverse Events will be summarised by treatment regimen and all other safety endpoints will be presented by listings and individual graphical representation only. Safety data consists of accumulated data from the trial.

4 References

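### The accumulated adverse-event summary by regimen has no denominator for exposure time or for tests done, although the two prophylaxis regimens differ in both

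*SAP*

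**What the plan says.** SAP 2.10, on part 2 of the Extension Phase: "Adverse events and consumption of N8-GP will be summarised based on accumulated data by treatment regimen". SAP section 3 (Safety data) repeats that "Adverse Events and Serious Adverse Events will be summarised by treatment regimen" and adds: "Safety data consists of accumulated data from the trial". SAP 2.3 gives the form of the summary: how many events, and how many patients had any event. No exposure-adjusted or per-assessment rate is specified.

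The part 2 visit schedule depends on the regimen. Under Protocol 5.3.1 (Amendment 15), patients who return to every-4-day dosing "attend visits every third month while on every 4 day treatment regimen". Protocol 8.1.4 (Amendment 15) states: "Whenever a patient in Extension phase part 2 switches to every 7 day prophylaxis, the home treatment period will be 4 weeks"; this lasts for four months, and the interval is 8 weeks after that. Patients already on every-7-day dosing in part 1 continue at 8 weeks. Table 2-3 places AE questioning, vital signs, inhibitor and binding-antibody tests, biochemistry and haematology at these visits.

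Test results reach the AE data. Clinically significant laboratory findings are AEs (Protocol 8.3.6). A single positive inhibitor test is a MESI, reported on an AE form (8.3.2.2 and 12.1.2, Amendment 6). Inhibitor formation always counts as an SAE (12.1, Amendment 18).

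**The concern.** Two regimens stand side by side in one safety table, and one of them is tested more often per year. If part of what the table counts is found only by testing, the columns differ even when the regimens are equally safe. The columns also cover different lengths of time, so without a denominator a reader cannot tell which way any distortion runs.

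The sponsor dealt with visit frequency elsewhere. Amendment 15 gave both randomised part 1 arms the same visits, explaining: "This is to avoid any bias in the randomised arms". The SAP regroups the part 2 PRO summaries "since timing of visits depend on treatment regimen and since patients are moving between treatment regimens", and limits the PK summary by visit for a similar reason. The AE summary has no corresponding provision.

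Apart from AEs and SAEs, safety data are to be shown only as listings and individual plots (SAP section 3). The AE/SAE table is therefore the main by-regimen safety summary in a phase whose stated aim includes long-term safety.

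**Working it through.** The plan attaches no figure to the AE summary, so there is nothing of its own to reproduce. The check compares tests per patient-year on the two regimens.

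**Inputs from the documents**
- Part 2, every 4 days: visits every 12 weeks (Protocol 5.3.1, 8.1.4).
- Part 2, every 7 days: visits at weeks 4, 8, 12 and 16 after a switch, then every 8 weeks; every 8 weeks throughout for patients continuing from part 1 (8.1.4).
- Main Phase: visits at weeks 4, 8, 12, then every 8 weeks to week 76 (Table 2-1). That is 5 visits by week 28, 8 by week 52 and 11 by week 76, or 11/76 × 52 = 7.5 per year.
- Part 1, 24 weeks: 5 visits in each randomised arm, 3 in the non-randomised group (Table 2-3).

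**Assumptions**
- Main Phase of 28, 52 or 76 weeks per patient.
- Part 2 of 143 weeks (to the SAP's 15 August 2017 cut) or 213 weeks (to the planned last visit in December 2018). Both imply a start in the last quarter of 2014, when the protocol expected part 1 to end.

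**Step 1: part 2 alone, tests per patient-year**
- Every 4 days: 52/12 = 4.33.
- Every 7 days, steady: 52/8 = 6.5; ratio 6.5/4.33 = 1.5.
- Every 7 days, first year after a switch: 4 + (52 − 16)/8 = 8.5; ratio 8.5/4.33 = 1.96.

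**Step 2: accumulated data, which is what the table uses**

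With M the Main Phase weeks, v its visits and P the part 2 weeks:
- Every 4 days: (v + 3 + P/12)/(M + 24 + P) × 52 if not randomised in part 1; replace 3 by 5 if randomised.
- Every 7 days since part 1: (5 + P/8)/(24 + P) × 52.

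| M | P | Every 4 days, not randomised | Every 4 days, randomised | Every 7 days | Ratios |
|---|---|---|---|---|---|
| 28 | 143 | 5.31 | 5.84 | 7.12 | 1.34, 1.22 |
| 28 | 213 | 5.05 | 5.45 | 6.94 | 1.37, 1.27 |
| 52 | 143 | 5.44 | 5.92 | 7.12 | 1.31, 1.20 |
| 52 | 213 | 5.17 | 5.53 | 6.94 | 1.34, 1.25 |
| 76 | 143 | 5.55 | 5.97 | 7.12 | 1.28, 1.19 |
| 76 | 213 | 5.27 | 5.61 | 6.94 | 1.32, 1.24 |

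The ratio is about 1.2 to 1.4. For a patient in the first year after a part 2 switch, 8.5 against 5.05 to 5.55 gives 1.5 to 1.7.

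**Step 3: crude number of tests per patient**
- On every 7 days since part 1, against non-randomised every 4 days: from 22.9/25.9 = 0.88 (M = 76, P = 143) to 31.6/25.8 = 1.23 (M = 28, P = 213).
- On every 7 days for one year only: from 8.5/31.8 = 0.27 to 8.5/19.9 = 0.43.

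Unadjusted counts can therefore lean towards either regimen.

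**Step 4: which events are affected**

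A silent finding lasting D weeks, with visits I weeks apart, is caught with probability min(1, D/I).
- D of 8 weeks or less: 8-weekly visits catch (D/8)/(D/12) = 1.5 times as many as 12-weekly visits.
- D of 4 weeks or less: 4-weekly visits catch 3 times as many as 12-weekly visits.
- D of 12 weeks or more: the ratio is 1.0; the finding is caught earlier, not more often.

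For false positives, the documents give no rate. At an assumed 0.1% to 2% per test, the chance of at least one in a part 2 year, 1 − (1 − q)^n, is 0.43% to 8.4% with n = 4.33, 0.65% to 12.3% with n = 6.5, and 0.85% to 15.8% with n = 8.5.

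**The case against.** The strongest reply is that the table is not a comparison. Part 2 plans no AE test or contrast. Regimen there is not randomised, and a move to every-7-day dosing requires few recent bleeds (Protocol 5.3.1). A comparison with equal visits already exists: SAP 2.10 gives separate part 1 AE summaries for the randomised subset. This stands, and it is why the fix names that subset as the reference. It does not make the accumulated columns readable side by side.

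The sponsor's remarks on visit timing also carry limited weight. The PK and PRO changes concern summarising by visit, and Amendment 15 speaks of bias in the randomised arms without naming AE detection. They show awareness of unequal schedules, not acceptance of this particular point.

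A reader might infer several stronger things that the documents do not support:
- *That the 1.5 to 2.0 ratio applies to the planned table.* The SAP's table pools the whole trial, and every-4-day time includes Main Phase time monitored at 7.5 visits per year. The larger ratio would apply only to a table of part 2 alone by regimen, which the SAP does not specify.
- *That every-7-day dosing will show more harms.* Step 3 shows that crude counts can go either way.
- *That the total AE rate is materially distorted.* At ratios of 1.2 to 1.4 the every-4-day shortfall is 17% to 29% (1 − 1/1.2; 1 − 1/1.4). To move the total by 10%, transient test-detected events would have to be about 34% to 59% of all AEs (10/29; 10/17). The documents give no share. Patients are asked about AEs since the previous visit and at every contact, so longer intervals lose little of what they notice.
- *That all examinations follow the 4-to-8 against 12-week pattern.* Physical examination is at every second numbered visit, about 16 against 24 weeks apart, and Amendment 19 describes the ECG as approximately yearly.
- *That the inhibitor incidence endpoint is affected by regimen.* It is evaluated on accumulated data and not stated by regimen, and a case needs two consecutive positive tests.

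**Conclusion.** The point holds in a limited form. The by-regimen AE/SAE summary gives counts across regimens that differ in exposure time and in test frequency. Per patient-year, every-7-day dosing has about 1.2 to 1.4 times the scheduled inhibitor and laboratory tests over the accumulated data, and 1.5 to 2.0 times within part 2. Rates of transient or false-positive test-detected events are not comparable between regimens, and the planned summary cannot show the direction of the difference. Persistent findings and patient-noticed AEs are little affected.

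The accumulated ratio rests on the assumed 28 to 76 weeks of Main Phase and 143 to 213 weeks of part 2, and on visits kept to schedule. It compares individual patients; the Main Phase time of patients who later moved to every-7-day dosing also falls in the every-4-day column and would lower the ratio. Nothing here shows a change in the trial's main conclusions. It is a cheap improvement to a descriptive table.

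**What to change.** Leave the visits unchanged. In SAP 2.10 (part 2) and section 3 (Safety data):

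1. Give by-regimen AE and SAE rates per patient-year, split by trial phase, beside the planned counts.
2. For events that are objectively test-detected (single-positive and confirmed inhibitor tests, central-laboratory abnormalities), also give events per 100 tests done on that regimen. Patient-year rates alone would leave the difference in tests per year in place.
3. State that any AE comparison between regimens rests on the randomised part 1 subset, where visit schedules were equal, and that the accumulated by-regimen table is descriptive.

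There is no need to classify every AE by whether a scheduled assessment found it; in an open-label trial that would add judgement after the fact.

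The cost is SAP wording and one or two extra tables from data already collected. The drawback is that inhibitor events will be few, so their per-test rates will be imprecise.

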2	n = additional visit number until end of trial
3	weeks since last visit
4	It is mandatory to attend 2 consecutive a-visits upon switching to every 7 day treatment regimen in order to achieve visits every 4 weeks (± 1 week) during the first 4 months. After this time period the patient must attend visits every 8 weeks (± 1 week) while on every 7 day treatment regimen.
5	Only in case of expected unexpected allergic/anaphylactic reaction
6	Only every second non a-visits, e.g. visit (V19, V21, V23...)
7	Antibody sample will only be drawn from patients in the on-demand arm if they received treatment since last visit
8	A wash-out period of minimum 96 hrs is needed before the sample
9	Trough to be sampled before dosing and recovery to be sampled 30 min (± 5 min) after dosing, only for prophylaxis patients
10	Only for patients in prophylaxis treatment
11	Only height every year for patients below 18 years, otherwise only BW
12	Only yearly (at V21, V25...)
13	Only to be taken if HIV status is positive
14	Assessment during unscheduled visit are not mandatory but can be performed

5 Trial Design

...

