2.9 Section 8.3.2.3 HCP antibodies

A selection of the samples collected for the N8-GP binding antibody analysis will be analysed for HCP antibodies. This analysis will be performed depending on the amount of sample available.

The analysis of HCP antibodies is planned to include samples taken at the following time points: pre-dose prior to first N8-GP exposure and hereafter approximately every 6-12 months.

If deemed necessary more samples may be analysed to fully characterise the individual patient's HCP antibody profile.

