The pre-dose FVIII activity levels assessed from after at least 4 PPX dosing intervals will be analysed to get an estimate of the pre-dose level for N8-GP at steady state. The model will be a mixed model on the logarithmic plasma activity levels with dose and age as a factor and patient as a random effect. Plasma concentrations below lower limit of quantification (LLOQ) will be set to half the value of the LLOQ. The estimated pre-dose FVIII level will be presented together with the 95% confidence intervals. Trial duration for the main phase differs between patients, but all patients reach at least Visit 8 prior to being transferred to Visit 13 (end of main phase). Therefore, the analysis will be performed both on pre-dose values from main and extension phase part 1 and furthermore including only pre-dose values up to visit 8.

A sensitivity analysis including all data after at least 4 PPX dosing intervals will also be performed for both cases.

Furthermore the same analyses will be performed for measurements from the randomised patients in the extension phase part 1.

Pre-dose activity, post-dose activity and incremental recovery will be summarised by visit. Furthermore, mean pre-dose activity and mean post-dose activity will be plotted vs. time.

In extension phase part 2, the only PK endpoint that will be summarised by visit is incremental recovery for all prophylaxis patients, since incremental recovery is independent of dose and dosing frequency. Incremental recovery will be calculated using the same activity measurements as used for estimation of recovery and trough levels.

In extension phase part 2 the following rules have been added to the rules for activity measurements listed above (the new rules are also applied to activity measurements from main and extension phase part 1)

- Samples from visits when changing treatment regimen (e.g. from every 4 day dosing to every 7 day dosing) will be excluded (this rule replaces the rule for randomised patients changing from every 7 day dosing to every 4 day dosing)
- Samples taken at “return visit” from the PK-trial (NN7088-4033) are excluded.
- If the FVIII activity is above 3.0 IU/ml based on one of the three clot assays and the ratio of Clot PSS (chrom)/Chrom PSS > 1.5, all clot data for this sample time point will be excluded. The reason for this rule is that plasma samples can be activated during pre-

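### Part 2 incremental recovery and anti-CHO HCP antibodies are tabulated by visit number, which stands for different times on drug under the every-4-day and every-7-day regimens

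*SAP*

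**What the plan says.** **Recovery.** SAP 2.10 plans the part 2 table quoted here: "Incremental recovery will be summarised by visit for extension phase part 2". SAP 2.2.4.1 pools the regimens: "the only PK endpoint that will be summarised by visit is incremental recovery for all prophylaxis patients". SAP 3 gives the reason for keeping this one measure by visit: recovery is dose-normalised, so a change of regimen or dose should not affect it.

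**HCP antibodies.** SAP 2.10: "For Anti-CHO HCP-antibodies, the number of negative/positive samples will be summarised by visit". SAP 2.4 says the same and lists HCP as exploratory. Protocol 8.3.2.3 (Amendment 19) sets the testing times by calendar: "pre-dose prior to first N8-GP exposure and hereafter approximately every 6-12 months". Testing uses a selection of stored samples, depends on the amount left, and may be extended for an individual patient.

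**Visit schedule.** Amendment 15 gave the two regimens different intervals. For a patient back on Q4D, Protocol 5.3.1 says to "attend visits every third month while on every 4 day treatment regimen". For Q7D, after the first 4 months following a switch, footnote 4 of Protocol Table 2-3 says: "After this time period the patient must attend visits every 8 weeks (± 1 week) while on every 7 day treatment regimen". Visit numbers run on in sequence when a patient changes regimen.

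**PROs.** SAP 3 says the part 2 PRO endpoints will be "summarised by grouping of time since first dose, since timing of visits depend on treatment regimen". SAP 2.10 makes these groups one year wide.

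**The concern.** After Amendment 15 a part 2 visit number no longer marks a time. Patients with the same number of visits have been on N8-GP for different lengths of time, depending on their regimen history. A by-visit row of pooled recovery averages over those times, and the mix of patients changes along the table. A slow fall in recovery with exposure would be blurred, and a change in who is still present could look like a trend.

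SAP 3 recognises the cause. It cites regimen changes and unequal visit intervals when it drops by-visit summaries of the other FVIII activity data. It drops the part 2-only bleeding rates because patients enter part 2 with different trial durations. It moves PROs to time since first dose. Recovery stays by visit for a reason that concerns dose, and no reason is given for HCP.

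The HCP table has a second weakness. Its unit is the sample, while the useful long-term figure is how many patients turned positive after starting N8-GP.

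**Working it through.** **Inputs**
- Q4D interval: 12 weeks (±2) since the last visit (Protocol Table 2-3 and 8.1.4, Amendment 15).
- Q7D interval between numbered visits: 8 weeks (±1), from the same places. After a switch to Q7D, two extra a-visits are slotted in, so Visits 17a, 18, 18a and 19 fall at weeks 4, 8, 12 and 16. The numbered visits stay 8 weeks apart.
- Ends of data: 15-Aug-2017 cut-off (SAP 2.5) and planned last visit 03-Dec-2018 (Protocol 7, Amendment 21).
- Start of part 2: not given. Assumed between 1 June and 31 December 2014.

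**The plan's own figure.** Protocol 8.4.5 treats Visits 21, 25 and so on as roughly a year apart. Four intervals on Q4D are 4 × 12 = 48 weeks (range 4 × 10 = 40 to 4 × 14 = 56), which fits. On Q7D they are 4 × 8 = 32 weeks (range 28 to 36), which does not.

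**Same row, different time.** Weeks since Visit 17 = (visit number − 17) × interval. The gap is (visit number − 17) × (12 − 8).

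| Visit | Q4D throughout | Q7D throughout | Gap, weeks |
|---|---|---|---|
| 18 | 12 | 8 | 4 |
| 21 | 48 | 32 | 16 |
| 25 | 96 | 64 | 32 |
| 30 | 156 | 104 | 52 |

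Visit windows do not close the gap: a Q4D interval is at least 10 weeks and a Q7D interval at most 9.

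**Spread already present at Visit 17.** These gaps count from Visit 17, not from first dose. The main phase ran from about 7 to about 27 months (Protocol 5.1). Adding the 24 weeks of part 1, about 5.5 months, puts time since first dose at Visit 17 at about 12.5 to 32.5 months. With the SAP's 100-week main-phase maximum (SAP 2.2.2), about 23 months, the upper end is about 28.5 months. So even patients on one regimen are not aligned by visit number.

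**Last row reached on one regimen throughout, at nominal intervals.** Last visit = 17 + whole number of (weeks available ÷ interval).

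| End of data | Weeks available | Q4D | Q7D |
|---|---|---|---|
| 15-Aug-2017 | 137 to 167 | V28 to V30 | V34 to V37 |
| 03-Dec-2018 | 205 to 235 | V34 to V36 | V42 to V46 |

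For example, 167 ÷ 12 gives 13 whole intervals (V30) and 167 ÷ 8 gives 20 (V37). Patients on Q4D throughout run out 6 to 10 visit numbers before patients on Q7D throughout. Allowing for one completed 12-week interval after a return to Q4D, a mostly-Q7D patient can still appear in the last row or the one before it.

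**HCP.** A patient normally gives one sample per visit, so repeated positives recur across rows. Pre-dose results fall in their own early rows. No row or sum of rows links a later positive to the same patient's pre-dose result.

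**The case against.** The best defence is that this was a considered choice on a descriptive table. SAP 2.2.4.1 says recovery does not depend on dose or dosing frequency, and SAP 3 shows that the sponsor thought about visit intervals before keeping only this measure. Recovery at scheduled visits is also listed (SAP 2.2.4) and plotted by production process and anti-PEG status (SAP 2.10). Protocol 8.3.2.1 has a patient-level check: new binding antibodies with recovery below 60% of the screening value, given enough pre-dose FVIII, prompt a repeat inhibitor sample. The main immunogenicity endpoint, inhibitor incidence, uses accumulated data and does not rely on visit numbers. All of this stands. It limits the consequence, but independence from dose is not independence from time on drug.

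Several stronger readings are tempting and not supported:
- That the late rows hold only Q7D patients. Numbering continues after a return to Q4D, so those rows can include patients now on Q4D. Among the part 2 rows, it is the a-visit rows that are confined to Q7D.
- That a fall in recovery could be seen only in this table, or that part 2 exists to collect these two measures. The listings, plots and patient-level check say otherwise, and the stated aim of part 2 is long-term safety and efficacy data in general.
- That repeated HCP positives pile up within a row, or that each row covers some known share of patients. The first is mainly an effect across rows. The second would need a testing pattern that the documents do not give.

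**Conclusion.** The point holds as a modest, cheap improvement. Both part 2 tables use an axis that the SAP itself judged unsuitable for PROs. For single-regimen patients the mismatch is 4 weeks per numbered visit, reaching a year at Visit 30, on top of unequal exposure at entry to part 2. The latest rows hold patients who spent most of part 2 on Q7D, some of whom may since have returned to Q4D. The HCP table cannot show how many patients became positive on N8-GP.

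The intervals come from the documents. The last-row figures rest on the assumed June to December 2014 start, on nominal intervals and on no switching. Switching blurs the split between regimens but does not restore a common time axis. No test, threshold or main conclusion is affected.

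**What to change.** Amend SAP 2.2.4.1, 2.4, 2.10 and 3.

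- **Incremental recovery, part 2:** tabulate by time since first dose in windows that suit its sampling, for example 6-monthly. State how several values from one patient in a window are combined, for example by the patient's mean, and show regimen at sampling. The one-year PRO groups are too wide for a measure taken at every visit and could hide a decline within a year.
- **HCP antibodies:** tabulate by time since first dose in yearly groups, which match the 6-12 month testing. Add a count of patients: positive before first dose; newly positive among those with a negative pre-dose sample; and no pre-dose sample, shown separately.
- **Consistency:** SAP 3 limits safety endpoints other than adverse events to listings and individual plots. Either exempt HCP there explicitly, or state that it is handled as exploratory under SAP 2.4.

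The cost is SAP wording and reprogramming of two descriptive tables, with no new data. The drawback is that the new tables will not compare directly with earlier by-visit ones.
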